In Chile, it has been identified that low socioeconomic and educational levels are social determinants of health that negatively impact, with higher rates of overweight, physical inactivity, hypertension, and diabetes observed in lower-income groups. These individuals often rely on the public health system.

Within the public health system, upon detecting these risk factors, individuals can access the Cardiovascular Health Program (CHP), which aims to reduce the incidence of cardiovascular events by controlling and compensating CRF in primary healthcare. This program offers comprehensive risk factor management, including access to clinical control, medications, and counseling on healthy lifestyles. Patients are classified according to their risk of having a cardiovascular event in the next ten years (CVR) as low, moderate, and high, with specific therapeutic goals set for each category.

Once the goals are defined according to the CVR level, a therapeutic management is established consisting of two phases: the compensation phase, aimed at achieving therapeutic goals, and the follow-up phase for the compensated patient. In the compensation phase, recommendations on healthy lifestyles are made, and

pharmacological treatment is prescribed according to the risk level. It is expected that in the first two to three months from joining the program and receiving medications, the patient will compensate their blood pressure, glycemia, glycated hemoglobin, and cholesterol levels. In the follow-up stage, controls are suggested according to an individualized intervention plan based on cardiovascular risk: high risk every 3 months, moderate risk every 6 months, and low risk every 6-12 months, either with a doctor, nurse, nutritionist, or senior nursing technician. Among the interventions to promote a healthy lifestyle, the promotion of regular moderate-intensity physical activity stands out.

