2.2.2 SPECIFIC OBJECTIVES

- Describe the effects of applying a personalized concurrent exercise prescription guide on cardiovascular risk factors in adult users of the Cardiovascular Health Program at CESFAM Externo de Valdivia.

- Describe the effects of applying a personalized concurrent exercise prescription guide on physical capacity in adult users of the Cardiovascular Health Program at CESFAM Externo de Valdivia.
- Evaluate adherence to the personalized concurrent exercise guide and pharmacological treatment in adult users of the Cardiovascular Health Program at CESFAM Externo de Valdivia.
- Describe the clinical significance of interventions through effect size calculation and perceived clinical relevance by participants regarding the interventions.

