Sample Size Calculation: The sample size calculation will be based on literature recommendations for pilot studies and includes:

1. T-test – Means: difference between two independent means
2. Type I error: 5%
3. Statistical power: 80%
4. Effect size (ES): 0.5 according to Cohen's classification. Using these parameters, the recommended total sample size is 15 subjects per group. Assuming a 30% dropout rate, the total population will be 39 participants. After the eligibility process, participants will be randomly assigned to an experimental group (EG) and a control group (CG) using a 1:1 ratio online system (<https://www.randomizer.org/>). Assignment concealment will be carried out by an investigator not involved in the clinical procedures of the RCT using opaque, sealed, and consecutively numbered envelopes. The random sequence and assignment concealment will control selection bias.

The experimental group will receive the intervention based on the personalized exercise prescription guide plus their usual pharmacological treatment associated with the CHP, and the control group will maintain their usual pharmacological treatment associated with the CHP.

Data Collection Techniques: All evaluations will be conducted pre- and post-intervention in the experimental and control groups.

Clinical Record Information Review: The CHP medical manager, with authorization from the CESFAM Externo management and approval from the Ethics Committee of the Valdivia Health Service, will review the clinical records of participants, gathering the following information:

- Sociodemographic and medical background: sex, age, education level, duration in the cardiovascular health program, comorbidities, medications, dosage, and duration of medication use. These variables will be used to characterize the study sample.

Cardiovascular Risk Factor Evaluation: Evaluations and user follow-up will be conducted by physical therapists trained in evaluation techniques, exercise prescription, and cardiovascular risk factors, at the Universidad San Sebastián Health Center located at [name], Valdivia. A physical therapist will measure variables and be blinded to the participant's intervention assignment.

Cardiovascular Variables Evaluation: Blood pressure (systolic and diastolic) and heart rate will be measured using an automatic monitor (Omron HEM 7130™) following the standard procedure in a seated position after 15 minutes of rest, conducted before and after the intervention.

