A two-way repeated measures ANOVA will be used to determine intra-group and inter-group differences. Model effects will include Group (CG and EG), Time (Pre-test, Post-test), and their interaction over time (Group x Time). Tukey's post hoc test will be used for variables with Group \times Time interaction. Data analysis will be conducted by an investigator blinded to the intervention groups. Intention-to-treat analysis will be considered using the multiple imputation method for handling missing data and incomplete datasets.

The clinical significance of the interventions will be determined by effect size using Cohen's "d" (<0.2 =negligible, $0.2-0.49$ =small, $0.5-0.79$ =moderate, ≥ 0.8 =large). The clinical relevance of interventions will be assessed based on perceived therapeutic changes by participants using the Global Rating Scale (GRS). The GRS will evaluate the intervention's impact on relevant domains from the user's perspective and experience, using a 15-point Likert scale (-7=much worse, 0=no change, +7=much better). Differences interpretation: 1-3 points=small, 4-5=moderate, 6-7=significant.

All statistical analyses will be conducted using SPSS version 26 (SPSS™ Inc., Chicago, IL, USA).

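### Clinical significance is read from the point estimate of an undefined Cohen's d, with no confidence interval or direction; at 15 per arm that label cannot carry the conclusion

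*Combined protocol and SAP*

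**What the plan says.** One of the four specific objectives in section 2.2.2 is to "Describe the clinical significance of interventions through effect size calculation", together with the relevance that participants themselves perceive. The Statistical Analysis text in section 2.3 is firmer: "The clinical significance of the interventions will be determined by effect size". It names Cohen's d and sets the bands ("<0.2 =negligible, $0.2-0.49$ =small, $0.5-0.79$ =moderate", with 0.8 and above called large). The same paragraph assigns perceived relevance to the Global Rating Scale (GRS), which has its own point bands.

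Nothing in the document says:

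- whether d is between arms or within an arm;
- whether it uses post-intervention values or change;
- which standard deviation divides it;
- whether its sign counts;
- whether it carries a confidence interval.

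The repeated-measures ANOVA covers both within-group and between-group differences, so it does not settle which d is meant. Section 1.2 says the programme classifies patients by risk, "with specific therapeutic goals set for each category", but the d bands are not linked to those goals or to mmHg or mg/dl.

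On size, section 2.3 bases the calculation on a t-test for the "difference between two independent means" and concludes that "the recommended total sample size is 15 subjects per group". It adds: "Assuming a 30% dropout rate, the total population will be 39 participants".

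**The concern.** The rule takes one number per variable and reads a clinical conclusion from the band it falls in. With 15 per arm, the sampling error of d is large relative to bands that are 0.2 to 0.3 wide. Chance alone will often move a variable with no effect into the small or moderate band. It will also often move a variable with a real effect of the planned size out of the right one.

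The missing direction matters because lower values are the favourable ones for all the primary variables. Exercise minus control would then give a negative d for a benefit. Read literally, the bands would file that as negligible. Read as absolute values, they would give a benefit and a harm of equal size the same label.

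At stake is the answer to part of a stated objective, and the way small observed differences in blood pressure, glucose and lipids are presented to readers.

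**Working it through.** **The plan's own figures.** With d = 0.5, 5% type I error and 80% power, n per arm = 2(1.96 + 0.84)²/0.5² = 63 two-sided (64 by exact t). One-sided it is 50 (51 by exact t). Neither gives 15. The total of 39 is 30 × 1.3. How 15 was reached is a separate matter; it is used here only as the planned size.

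**Chance of each label with no true effect.** For normal data and a between-arm d on unadjusted post values, d = t × √(1/n₁ + 1/n₂) with n₁ + n₂ − 2 degrees of freedom. At 15 per arm, √(2/15) = 0.365 with 28 df.

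| Cut-off for d | t needed | Either direction | Favouring exercise |
|---|---|---|---|
| 0.2 | 0.2/0.365 = 0.548 | 58.8% | 29.4% |
| 0.5 | 0.5/0.365 = 1.369 | 18.2% | 9.1% |
| 0.8 | 0.8/0.365 = 2.191 | 3.7% | 1.8% |

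**Other analysed sizes (0.2 cut-off, either direction).** Allocation is 1:1 ("using a 1:1 ratio online system").

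- All 39 analysed, 19 and 20 per arm: 53.6%.
- 39 less 30% (39 × 0.7 = 27.3), 13 and 14 per arm: 60.8%.

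**Other definitions of d (0.2 cut-off, either direction, 15 per arm, simulation).** The documents give no pre-post correlation, so those used below are assumptions.

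| Definition | Correlation 0.5 | 0.7 | 0.8 |
|---|---|---|---|
| Baseline-adjusted difference / pooled baseline SD | 54% | 46% | 38% |
| Between-arm difference in change / pooled baseline SD | 59% | 48% | 39% |
| Between-arm difference in change / SD of change | 59% | 59% | 59% |
| Within-arm change / baseline SD | 45% | 33% | 24% |
| Within-arm change / SD of change | 45% | 45% | 45% |

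**Precision of an observed d.** By the noncentral t at 15 per arm, an observed 0.2 has a 95% CI of about -0.52 to 0.92. An observed 0.5 has about -0.23 to 1.22, a span of 1.22 + 0.23 = 1.45. That interval reaches every band. Two-sided p < 0.05 needs an absolute d of about 2.048 × 0.365 = 0.75, so every small label, and most of the moderate band, goes with an interval that includes zero.

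**If the true d is 0.5, as planned (post values, 15 per arm).** The estimate falls below 0.2 in 20% of trials, reaches 0.8 or more in 22%, and lands in the moderate band in 28%.

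**The case against.** The strongest reply is that these are conventional descriptive bands in a declared pilot. Section 2.2.2 says only that clinical significance will be described, group differences are tested separately by t-test and ANOVA, and the GRS gives the patient's view. Much of this stands. No passage makes a band a criterion for success, efficacy or progression, so a reader who inferred that the trial's conclusion turns on d would go further than the text. The GRS does answer the other half of the objective. What remains is that the analysis text lets d determine clinical significance, and the GRS places no condition on that label.

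Three further inferences are tempting and not supported:

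- **That most variables would be labelled as at least a small benefit by chance.** The 59% counts both directions; in favour of exercise it is 29%. Even the two-sided figure is below half under several definitions of d that the text allows.
- **That a null trial would almost surely show some favourable label.** Over five primary measures (systolic and diastolic pressure, glucose, cholesterol, triglycerides), 1 − (1 − 0.294)⁵ = 82% for 0.2 or more and 1 − (1 − 0.091)⁵ = 38% for 0.5 or more. Both need independence, which is implausible when systolic and diastolic pressure come from one measurement. At an assumed common correlation of 0.5 they are about 63% and 27%.
- **That labels should be withheld unless the interval excludes zero.** That needs an absolute d of about 0.75, so small could never be used. With a true d of 0.5, about 74% of variables would go unlabelled (power 26%).

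Nor do the documents supply a between-arm minimum important difference. Section 1.2 mentions patient-level goals by risk category, without figures.

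**Conclusion.** The point holds in a limited form. As written, the rule derives clinical significance from the point estimate of a d that is undefined and unsigned and has no interval. At this sample size the resulting label is weak evidence of anything clinical. The headline sizes (59% and 18% in either direction, 29% and 9% in favour) assume normal data, 15 analysed per arm, no true effect and unadjusted post values. The spread across definitions, 59% down to 24% at assumed correlations of 0.5 to 0.8, shows that leaving d open is part of the problem, because the same data could earn different labels. The interval around an observed d of 0.5 settles the matter without appeal to the null: a moderate label is compatible with no effect and with a large one.

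This is a defect of interpretation and reporting. It does not invalidate the planned tests.

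**What to change.** In the Statistical Analysis text of section 2.3, replace the sentence that lets effect size determine clinical significance with wording such as:

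> Clinical significance will be described by the between-arm, baseline-adjusted difference in natural units (mmHg, mg/dl) with its 95% CI, together with the between-arm Cohen's d (that difference divided by the pooled baseline SD, signed so that positive favours exercise) with its 95% CI. The bands for d are descriptive, are always shown with the CI, and are not by themselves evidence of clinical significance.

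Keep the GRS as the separate patient-reported half of the objective. Do not add a rule that withholds labels unless the interval excludes zero. If the investigators can justify a minimum important difference for a variable, it may be stated before unblinding; the documents provide none, so this is optional and would take work of its own.

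The cost is a paragraph of wording, a baseline-adjusted estimate for each variable and extra table columns. No visits, measurements or participants are added. The downside is that fewer results can be presented as clinically significant.

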2.4 ETHICAL IMPLICATIONS ANALYSIS

Risk-Benefit Analysis: This study adheres to the Declaration of Helsinki, ensuring that all participants provide informed consent before commencing the project. The intervention will be conducted in both experimental and control groups. Evaluations will include health status (through clinical record review), cardiovascular parameters, metabolic parameters, and physical capacities. These activities present minimal risk to participants. The intervention has been carefully designed to ensure safety, respecting the user's right to withdraw from the test and/or exercise program at any time. However, users may experience post-exercise muscle fatigue, which could last up to 48 hours. To mitigate this risk, education on exercise effects will be provided. Safety criteria for not engaging in physical exercise have been established based on the Ministry of Health's physical activity recommendations for individuals with comorbidities.

Benefits include updating knowledge on participants' health status and physical capacity. Personalized physical exercise has been demonstrated as an effective tool for controlling cardiovascular risk factors, such as reducing blood pressure, improving glycemic control, lipid profile, and physical function. Consequently, the intervention presents a favorable risk-benefit balance due to minimal exposure to risk situations and the positive effects of personalized physical exercise.

Confidentiality Protection: The clinical record review will be conducted at CESFAM Externo by the CHP manager, and physical evaluations will be performed at the Universidad San Sebastián Health Center facilities, located at [name], Valdivia, by the research team. Each participant will be assigned a unique code to preserve anonymity. The informed consent will clarify that their data will not be used for purposes other than the study. The information collected will be stored in a database by the Principal Investigator for four years, after which it will be handed over to CESFAM. This information will be kept both in digital format on the Principal Investigator's equipment and in physical format, in file cabinets, within the Universidad San Sebastián, Valdivia campus, [name]. To prevent misuse of data, only the research team will have access to the results, upon request to the Principal Investigator.

References

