- If the participant does not reach the mark, they will be asked to reduce the pace for a valid test without stopping the time.

Scoring: The score will be the total number of complete steps in 2 minutes, counted as the number of times the right knee reaches the set height. Only one attempt will be made on the test day.

Safety norms: Participants with balance issues should be near a wall or chair for support in case of balance loss. The examiner will supervise all participants for signs of excessive exertion. After the test, participants will walk slowly for one minute.

The equation to estimate peak oxygen consumption is: $VO_2 (\text{mLkg}^{-1}\text{min}^{-1}) = 13.341 + 0.138 * \text{total steps} - (0.183 * \text{BMI})$.

Body Composition: Height will be measured with a precision stadiometer (Seca Bodymeter 206), and weight, fat mass percentage, and lean mass percentage will be measured using a bioimpedance meter (TANITA BC-534). BMI will be estimated using the formula kg/m².

Treatment Adherence: Adherence to the treatment refers to the degree to which participants follow the prescribed physical exercise guide. This variable will be operationalized as compliance with at least 70% of the scheduled exercise sessions.

Measurement Method: Adherence will be measured using two primary mechanisms:

1. **Biweekly Phone Calls:** A follow-up protocol will be established, with calls made every two weeks to participants to gather self-reported compliance data with exercise sessions. These interactions will also identify potential barriers or facilitators of adherence, allowing proactive adjustments to the intervention if necessary.
2. **Exercise Logbooks Review:** Each participant will maintain a detailed logbook of exercise sessions performed, including date, duration, and type of exercise. Reviewing these records will provide an objective measure of adherence, complementing the data obtained through phone calls.

Adherence Criteria: A participant will be considered "adherent" if they comply with at least 70% of the scheduled exercise sessions, calculated by dividing the number of completed sessions by the total number of scheduled sessions and multiplying the result by 100.

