Aerobic Exercise: Participants will perform 5-10 intervals/session of walking or jogging at moderate to high intensity, with a rating of 5 to 8 points on the modified Borg scale (1-10 points). Each interval will consist of 1 minute of walking or jogging, followed by 2 minutes of inactive rest. Every 2 weeks, the load (cadence) will be adjusted due to normal physiological adaptations, always exercising at an intensity of 5-8 points on the modified Borg scale, similar to previous studies.

Muscular Resistance Exercise: Participants will perform concentric, eccentric, and/or isometric contractions for 1 minute at an intensity of 5-10 according to the OMNI-RES scale. The rest period will last 2 minutes, and each exercise will be repeated 3 times. Three exercises will be performed per session: squats, push-ups, and planks. Exercise difficulty (load) will be adjusted according to the user's abilities. The exercise load may be modified every two weeks according to the physiological adaptations of

the subjects, to adjust the loads to the new thresholds, always working at an intensity of 5-10 on the OMNI-RES scale.

Pharmacological Treatment: Participants will be asked to maintain their lifestyle, including taking prescribed medications as usual.

Participants will be asked to complete a "control diary" with the sessions and exercises performed during the intervention, noting any medication changes, illnesses, and additional physical activity.

Control Group: Pharmacological treatment.

Participants in the control group will be asked to maintain their current lifestyle and exercise habits throughout the study, including taking prescribed medications as usual. They will complete a "control diary" to note any exercise, medication changes, illnesses, and relevant information. Once control participants complete post-intervention evaluations, they will be offered the opportunity to complete the same intervention as the exercise group.

Statistical Analysis: In this study, dependent variables will be described using mean and standard deviation. Normality and homoscedasticity assumptions will be verified using the Shapiro-Wilk test for all data.

To identify group differences at baseline and post-intervention, the Student's t-test for independent samples will be used, complemented by Levene's test for variance comparison between groups.

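### Section 2.4 calls the exercise intervention's risk-benefit balance favourable, but no planned data collection asks about adverse events and no by-arm safety summary is planned

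*Combined protocol and SAP*

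**What the plan says.** Section 2.3 fixes the content of each contact between the two assessments.

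- **Calls** (Treatment Adherence): "calls made every two weeks to participants to gather self-reported compliance data with exercise sessions". The text adds: "These interactions will also identify potential barriers or facilitators of adherence".
- **Logbooks** (Treatment Adherence): sessions performed, "including date, duration, and type of exercise".
- **Experimental-group diary** (Intervention): sessions and exercises done, "noting any medication changes, illnesses, and additional physical activity".
- **Control-group diary** (Intervention): participants are asked "to note any exercise, medication changes, illnesses, and relevant information".

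The Study Variables paragraph lists no safety outcome. The Statistical Analysis text covers the dependent variables, Cohen's d and the Global Rating Scale.

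Resistance work is prescribed with participants "always working at an intensity of 5-10 on the OMNI-RES scale". Aerobic intervals are set lower, at 5 to 8 on a 10-point modified Borg scale.

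Section 2.4 lists the evaluations and then says "These activities present minimal risk to participants". It names muscle fatigue of up to 48 hours as the only expected harm, refers to Ministry of Health safety criteria for when a person should not exercise, and concludes that the intervention's balance of risk and benefit is favourable.

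**The concern.** Participants are physically inactive, with a BMI of 25 to 39.9, and the inclusion list names treated hypertension, type 2 diabetes and dyslipidaemia. They receive a written prescription followed up by telephone. No supervision of the exercise sessions is described; the only stated watch for excessive exertion is during the step test. Whatever happens in those sessions reaches the dataset only if some form or call asks for it.

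Followed as written, the trial would report its efficacy variables with no structured harms data. A reader could then take the absence of recorded events as evidence of safety. The section 2.4 judgement would rest on prior evidence alone, and events missed during the six weeks could not be recovered reliably afterwards. This matters soon, because controls are to be offered the same programme after their final evaluation.

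Withdrawals add to the problem. The plan allows for 30% dropout and considers multiple imputation, but does not provide for recording why people leave. Someone who stopped after an injury could appear in the results only as an imputed value.

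**Working it through.** The plan states no expected event rate, safety precision or stopping limit, so there is no figure of its own to reproduce. The main check sets the planned sources side by side.

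| Source (section 2.3) | Content | Asks about adverse events? | Same in both arms? | Analysis planned? |
|---|---|---|---|---|
| Biweekly call | Session compliance; barriers and facilitators | No; an event may surface as a barrier | Not stated; the content concerns scheduled sessions, which controls do not have | Adherence threshold of 70% only |
| Logbook | Date, duration, type | No | Not stated; as above | Adherence only |
| Experimental diary | Sessions, drug changes, illnesses, extra activity | No; illness entries catch some | No | None |
| Control diary | Exercise, drug changes, illnesses, an open item for anything relevant | No; illness and open entries catch some | No; only this diary has the open item | None |
| Global Rating Scale | Perceived change, -7 to +7 | No; a net rating, not events | Not stated | Yes, as perceived change |

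No row has an adverse-event question, and no row leads to a safety table by arm. An injury, a fall or a hypoglycaemic episode is not clearly an illness, so the diary wording cannot be relied on to bring these out.

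A second check asks how much a complete collection could show.

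**Inputs** (Sample Size Calculation): 15 per group; 39 in total (2 × 15 × 1.3 = 39); 1:1 allocation, hence 19 and 20 per arm.

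**Formula**: with 0 events in n participants, the exact two-sided 95% upper limit is 1 − 0.025^(1/n).

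- n = 15: 1 − 0.025^(1/15) = 0.218
- n = 19: 1 − 0.025^(1/19) = 0.176
- n = 20: 1 − 0.025^(1/20) = 0.168

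The chance of seeing at least one event is 1 − (1 − p)^n. The documents give no p, so these risks are assumptions:

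| Assumed risk per participant | n = 15 | n = 19 |
|---|---|---|
| 1% | 14% | 17% |
| 5% | 54% | 62% |
| 10% | 79% | 87% |

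These figures describe the limits that the trial's size sets. They do not measure the missing collection, and they would remain after the fix. Without structured collection, no such interval can be calculated at all.

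**The case against.** The best defence is that section 2.4 is an advance ethics justification from prior evidence. No objective in section 2.2 claims to establish safety. The plan also has real safeguards: exclusion of ischaemic disease or arrhythmia, bone disease, chronic respiratory disease and uncontrolled chronic disease; no insulin-dependent diabetes; education on the effects of exercise; Ministry-based safety criteria; and resistance difficulty adjusted to ability. Both diaries record illnesses and drug changes, and an injury that stops exercise could well be mentioned as a barrier on a call.

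All of this stands. It lowers the expected risk and gives some informal capture. It does not supply a comparison: the entries are unprompted, the diary wording differs by arm, and no analysis is planned. A small pilot cannot establish safety, but that is a reason to collect events and report wide intervals.

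Four stronger readings are tempting, and the documents do not support them.

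- *The minimal-risk sentence is a claim about the exercise.* It directly follows the list of evaluations and most naturally refers to them. The later risk-benefit sentence is the one that concerns the intervention.
- *All the exercise goes to the top of the effort scale.* Only the resistance range reaches 10, and the documents do not print the end points of OMNI-RES, so 10 as its top is an assumption. The aerobic range stops at 8 of 10.
- *Events have no route to the investigator.* Barrier questions and illness entries are partial routes, and the removed consent and contact pages may hold reporting instructions.
- *The intervention is unsafe.* Nothing in the documents shows this.

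**Conclusion.** The point holds as a gap in data collection and analysis. The content of the calls, logbooks, diaries, variable list and statistical analysis is set out, and none of them solicits adverse events or tabulates them by arm. The trial's own data therefore cannot inform the statement that the intervention's risk-benefit balance is favourable. The efficacy estimates are not invalidated by this.

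The size of the gap cannot be put as a number, because the plan gives no event rate. What can be said is that even perfect collection with no events would leave upper limits of about 17% to 18% with 20 or 19 participants in an arm, and about 22% with 15. This assumes that allocation splits 39 as 19 and 20, and that the sessions are largely unsupervised, which is inferred from the written prescription and telephone follow-up rather than stated. It also assumes that the removed pages contain no structured event form; planned outcomes and analyses would in any case belong in section 2.3, which is present.

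**What to change.** 1. Put the same short checklist in the diary of both arms: injury, fall, symptoms of hypoglycaemia, chest symptoms, any other event, and whether medical attention was sought. Define an adverse event and a serious event beforehand.
2. Have someone other than the blinded assessor collect and review it. Use the biweekly call for this only if calls are made equally often to both arms.
3. Record the reason for every withdrawal.
4. Report, by arm, the number of participants with any event and with any serious event over the randomised six weeks, with exact two-sided 95% intervals. Use all randomised participants as the denominator and show how many returned the checklist.
5. Limit any safety statement to what those intervals support.

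The cost is a few more diary lines, slightly longer calls where calls are used, and one table. Two downsides need handling. Calls to controls may be new contact that alters the usual-care comparison; leaving the checklist in the diary avoids this. Talk of exercise-related events at the final visit could unblind the assessor, hence the separate collector. No change to exercise dose or to any clinical rule is proposed.
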